## 15.0 SAFETY REPORTING OF ADVERSE EVENTS

### 15.1 Adverse Events

An adverse event (AE) is defined as any new untoward medical occurrence or worsening of a preexisting medical condition in a clinical investigation participant administered study drug and that does not necessarily have a causal relationship with this treatment. An AE can therefore be any unfavorable and unintended sign (such as an abnormal laboratory finding), symptom, or disease temporally associated with the use of investigational product, whether or not considered related to the investigational product.

#### 15.1.2 Causality (Attribution) of Adverse Events

The investigator is to assess the causal relation of all AEs (i.e., whether there is a reasonable possibility that the study drug caused the event) using the following definitions:

Not Related:	Another cause of the AE is more plausible; a temporal sequence cannot be established with the onset of the AE and administration of the investigational product; or, a causal relationship is considered biologically implausible.
Unlikely:	The current knowledge or information about the AE indicates that a relationship to the investigational product is unlikely.

**Possibly Related:** There is a clinically plausible time sequence between onset of the AE and administration of the investigational product, but the AE could also be attributed to concurrent or underlying disease, or the use of other drugs or procedures. Possibly related should be used when the investigational product is one of several biologically plausible AE causes.

**Related:** The AE is clearly related to use of the investigational product.

Adverse events can be spontaneously reported or elicited during open-ended questioning, examination, or evaluation of a subject. (In order to prevent reporting bias, subjects should not be questioned regarding the specific occurrence of one or more AEs.)

Any other AE not listed as an expected event in the Investigator's Brochure or in this protocol will be considered unexpected.

### 15.1.3 Serious Adverse Events

A Serious Adverse Event (SAE) is any untoward medical occurrence that at any dose:

- Results in **death**
- Is **life-threatening** (defined as an event in which the participant was at risk of death at the time of the event; it does not refer to an event which hypothetically might have caused death if it were more severe)
- Requires inpatient **hospitalization or causes prolongation of existing hospitalization** (see NOTE below)
- Results in **persistent or significant disability/incapacity**
- Is a **congenital anomaly/birth defect**
- Is an **important medical event** (defined as a medical event(s) that may not be immediately life-threatening or result in death or hospitalization but, based upon appropriate medical and scientific judgment, may jeopardize the subject or may require intervention [e.g., medical, surgical] to prevent one of the other serious outcomes listed in the definition above.) Examples of such events include, but are not limited to, intensive treatment in an emergency room or at home for allergic bronchospasm; blood dyscrasias or convulsions that do not result in hospitalization.)
- Suspected **transmission of an infectious agent** (e.g., pathogenic or nonpathogenic) via the study drug is an SAE.

Although pregnancy, overdose, potential drug-induced liver injury (DILI), and cancer are not always serious by regulatory definition, these events must be handled as SAEs.

Any component of a study endpoint that is considered related to study therapy should be reported as an SAE (e.g., death is an endpoint, if death occurred due to anaphylaxis, anaphylaxis must be reported).

All Serious Adverse Events (SAEs) that occur following the subject's written consent to participate in the study through 100 days after discontinuation of dosing must be reported to BMS Worldwide Safety, whether related or not related to study drug. If applicable, SAEs must be collected that relate to any later protocol-specified procedure (e.g., a follow-up skin biopsy).

Following the subject's written consent to participate in the study, all SAEs, whether related or not related to study drug, are collected, including those thought to be associated with protocol-specified procedures. The investigator should report any SAE occurring after these aforementioned time periods, which is believed to be related to study drug or protocol-specified procedure.

If the investigator believes that an SAE is not related to study drug, but is potentially related to the conditions of the study (such as withdrawal of previous therapy or a complication of a study procedure), the relationship should be specified in the narrative section of the SAE Report Form.

NOTE: (PI determines if this information regarding hospitalizations are considered SAEs and should be included in the protocol. This is supplemental information that is included in BMS sponsored trials)

The following hospitalizations will not be considered SAEs:

- A visit to the emergency room or other hospital department < 24 hours, that does not result in admission (unless considered an important medical or life-threatening event)
- Elective surgery, planned prior to signing consent
- Admissions as per protocol for a planned medical/surgical procedure
- Routine health assessment requiring admission for baseline/trending of health status (e.g., routine colonoscopy)
- Medical/surgical admission other than to remedy ill health and planned prior to entry into the study. Appropriate documentation is required in these cases.
- Admission encountered for another life circumstance that carries no bearing on health status and requires no medical/surgical intervention (e.g., lack of housing, economic inadequacy, caregiver respite, family circumstances, administrative reason).
- Admission for administration of anticancer therapy in the absence of any other SAEs

### 15.1.4 Adverse Events of Special Interest

#### 15.1.4.1 What is considered an adverse event of special interest?

Adverse events of special interest (AESI) requiring expedited reporting by the investigator have been defined for this protocol. These are:

- Hemophagocytic lymphohistiocytosis (HLH; also known as histiocytosis haematophagic)
- Drug reaction with eosinophilia and systemic symptoms (DRESS) syndrome

#### 15.1.4.2 Reporting Timeframe

These AESI, whether related or not related to study drug, must be reported to BMS or designee within 24 hours of awareness of the event. These AESI are medically important events and are therefore considered SAEs. The reporting system for SAEs should be used (See Section 15.2).

#### 15.1.4.3 Diagnostic Scoring Criteria

HLH and DRESS syndrome may both pose diagnostic challenges due to varying clinical manifestations and signs and symptoms that may overlap with other clinical events. To assist investigators in identifying constellations of clinical symptoms that may be consistent with one of these diagnoses, standardized scoring criteria are provided. Formal evaluation and documentation of diagnostic scores based on these systems is not required; investigators should use their best clinical judgement as informed by these provided criteria to determine if a participant has experienced one of these AESI.

### 15.1.5 Non-Serious Adverse Event

- Non-serious Adverse Events (AE) are to be provided to BMS in aggregate via interim or final study reports as specified in the agreement or, if a regulatory requirement [e.g., IND US trial] as part of an annual reporting requirement.
- Non-serious AE information should also be collected from the start of a placebo lead-in period or other observational period intended to establish a baseline status for the subjects.

A **non-serious adverse event** is an AE not classified as serious.

#### 15.1.5.1 Non-Serious Adverse Event Collection and Reporting

The collection of non-serious AE information should begin at initiation of study drug. All non-serious adverse events (not only those deemed to be treatment-related) should be collected continuously during the treatment period and for a minimum of 100 days following the last dose of study treatment.

Non-serious AEs should be followed to resolution or stabilization, or reported as SAEs if they become serious. Follow-up is also required for non-serious AEs that cause interruption or discontinuation of study drug and for those present at the end of study treatment as appropriate.

### 15.1.6     Laboratory Test Abnormalities

All laboratory test results captured as part of the study should be recorded following institutional procedures. Test results that constitute SAEs should be documented and reported to BMS as such.

The following laboratory abnormalities should be documented and reported appropriately:

- Any laboratory test result that is clinically significant or meets the definition of an SAE
- Any laboratory abnormality that required the participant to have study drug discontinued or interrupted
- Any laboratory abnormality that required the subject to receive specific corrective therapy.

It is expected that wherever possible, the clinical rather than laboratory term would be used by the reporting investigator (e.g., anemia versus low hemoglobin value).

### 15.1.7     Pregnancy

If, following initiation of the investigational product, it is subsequently discovered that a study participant is pregnant or may have been pregnant at the time of investigational product exposure, including during at least 5 half-lives after product administration, the investigational product will be permanently discontinued in an appropriate manner (e.g., dose tapering if necessary for participant).

The investigator must immediately notify [contact] of this event via MedWatch or appropriate Pregnancy Surveillance Form in accordance with SAE reporting procedures.

Protocol-required procedures for study discontinuation and follow-up must be performed on the participant.

Follow-up information regarding the course of the pregnancy, including perinatal and neonatal outcome and, where applicable, offspring information must be reported on the MedWatch or a BMS Pregnancy Surveillance Form. A BMS Pregnancy Surveillance Form may be provided upon request.

Any pregnancy that occurs in a female partner of a male study participant should be reported to BMS. Information on this pregnancy will be collected on the Pregnancy Surveillance Form. In order for Sponsor or designee to collect any pregnancy surveillance information from the female partner, the female partner must sign an informed consent form for disclosure of this information.

### **15.1.8 Potential Drug Induced Liver Injury (DILI)**

Wherever possible, timely confirmation of initial liver-related laboratory abnormalities should occur prior to the reporting of a potential DILI event. All occurrences of potential DILIs, meeting the defined criteria, must be reported as SAEs (section 15.2).

Potential drug induced liver injury is defined as:

1. AT (ALT or AST) elevation > 3 times upper limit of normal (ULN), AND
2. Total bilirubin > 2 times ULN, without initial findings of cholestasis (elevated serum alkaline phosphatase), AND
3. No other immediately apparent possible causes of AT elevation and hyperbilirubinemia, including, but not limited to, viral hepatitis, pre-existing chronic or acute liver disease, or the administration of other drug(s) known to be hepatotoxic.

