In summary, BMS-986205 at 100 mg QD achieves trough plasma concentrations that exceed the human whole blood IC90, produces substantial serum kynureneine reductions similar to those observed at higher dose levels, demonstrates target engagement in the tumor microenvironment, appears (in combination with nivolumab) to have a more favorable tolerability profile compared to higher doses and overall similar to that of nivolumab monotherapy, and demonstrates clinical activity in combination with nivolumab[24]. Based on this evidence, BMS-986205 100 mg QD is the recommended phase 2 Dose (RP2D) in combination with nivolumab. For this study, we have chosen 50 mg QD as the starting dose level to be given with nivolumab 240mg to observe hepatotoxicity in an HCC population. BMS-986205 will be escalated to 100 mg QD with nivolumab when dose 1 level is shown to be tolerated.

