## 4.0 SUBJECT SELECTION

### 4.1 Inclusion Criteria

Patients must meet all of the following criteria to be eligible for study entry.

1. Men and women  $\geq 18$  years of age at the time of study entry.
2. Willing and able to provide written informed consent for the trial.
3. Life expectancy  $>12$  weeks.
4. Histologically or imaging confirmed hepatocellular carcinoma (mixed hepatocellular/cholangiocarcinoma or fibrolamellar subtypes are excluded).
5. Have disease that is not amenable for curative treatment approach.
6. Have measurable disease based on RECIST v1.1.
7.  $\geq 1$  liver lesions accessible for core biopsy that was either not previously treated by liver-directed therapy or progressed following liver-directed therapy.
8. Child-Pugh score of A.
9. ECOG performance status of 0 or 1.
10. Adequate hematology parameters:
  - a. Absolute neutrophil count (ANC)  $\geq 1000$  cell/mm $^3$
  - b. Platelet count  $\geq 50,000$ /mm $^3$
  - c. Hemoglobin (Hgb)  $\geq 8$  g/dL
11. Acceptable blood chemistry levels:
  - a. AST/SGOT, ALT/SGPT  $\leq 5$  x upper limit of normal (ULN)
  - b. Total bilirubin  $\leq 2$  ULN
  - c. Creatinine  $\leq 2$  x ULN
12. Subjects with active hepatitis B virus (Hep B) are allowed if antiviral therapy for hepatitis B has been given for  $>8$  weeks and viral load is  $<100$  IU/ml prior to first dose of trial treatment. Subjects with untreated hepatitis C virus (HCV) are allowed.
13. Willingness to undergo mandatory pre-treatment biopsy (unless there is adequate archival tumor specimen available) and mandatory on-treatment biopsy.

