### **5.5.3 Protocol-Specific Recommendation for Management of Hepatic Events**

Subjects with advanced HCC generally have underlying cirrhosis with decreased hepatic function. They may also have a concomitant chronic viral infection. For this study, the upper limits for inclusion were therefore adjusted to account for baseline liver dysfunction. Subjects with AST or ALT elevations within the CTCAE Grade 2 range are allowed to enroll in the study. This requires a protocol-specific approach for the management of hepatic events outlined as follows:

- Both BMS-986205 and nivolumab should be delayed for
  - Grade  $\geq 2$  toxicity in subjects with baseline AST or ALT within normal limit,
  - Grade  $\geq 3$  toxicity in subjects with baseline AST or ALT within grade 1 toxicity range
  - Drug related increase in AST or ALT at 2x baseline value or when AST or ALT is 8x ULN (whichever is lower) in subjects with baseline AST or ALT in grade 2 toxicity range.
- If AST or ALT levels do not improve with a dose delay of 3 - 5 days or if the levels worsen, initiate steroid therapy at 0.5 - 2 mg/kg/day methylprednisolone or oral equivalent.
- For ALT or AST levels  $> 8x$  ULN, initiate steroid therapy promptly at 1 - 2 mg/kg/day methylprednisolone or oral equivalent
- For all subjects initiating steroids, consult the PI within 24 hours after initiation of steroids. Gastroenterology consult is recommended.
- If AST or ALT levels do not improve within 3- 5 days or the levels worsen after the start of steroid therapy, discuss with the PI the possibility of adding mycophenolate mofetil at 1 g BID.
- Tapering of steroids can start once AST or ALT levels have declined by one CTCAE grade. Taper steroids slowly over no less than 1 month.

As outlined in above, nivolumab and BMS-986205 therapy may resume when AST or ALT have returned to patient's baseline unless the criteria for permanent discontinuation are reached. Subjects who require delay of therapy should be re-evaluated weekly or more frequently if clinically indicated. It is recommended to monitor elevations in AST or ALT approximately every 3-5 days until levels peak or begin to decline. Both therapies can be resumed when re-treatment criteria are met. The PI must be consulted prior to resuming nivolumab for all subjects who required steroid intervention. Tumor assessments for all subjects should continue as per protocol even if study drug dosing is delayed.

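### The potential-DILI SAE definition is not adapted to the HCC population: read literally, liver disease or viral hepatitis present at entry can keep a drug-related event off the expedited route

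*Combined protocol and SAP*

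**What the plan says.** Section 15.1.8 defines potential DILI by three conditions that must all hold. The first is ALT or AST more than three times ULN. The second is bilirubin more than twice ULN, provided alkaline phosphatase is not raised at the outset. The third is an alternative-cause condition: "No other immediately apparent possible causes of AT elevation and hyperbilirubinemia, including, but not limited to, viral hepatitis, pre-existing chronic or acute liver disease". Hepatotoxic co-medication is named there too.

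The consequence is stated in the same section: "All occurrences of potential DILIs, meeting the defined criteria, must be reported as SAEs". Section 15.1.3 adds that potential DILI is to be handled as an SAE even though it is not always serious by the regulatory definition.

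Section 4.1 admits active hepatitis B that has been treated for more than 8 weeks with viral load below 100 IU/ml. Of hepatitis C it says: "Subjects with untreated hepatitis C virus (HCV) are allowed". It allows AST and ALT up to 5 x ULN and total bilirubin up to 2 x ULN. Section 5.5.3 describes the population: "Subjects with advanced HCC generally have underlying cirrhosis with decreased hepatic function. They may also have a concomitant chronic viral infection". It then sets baseline-dependent rules for hepatic dose delay.

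Section 6.1.4 lists concurrent AST or ALT above 3 x ULN and total bilirubin above 2 x ULN among the drug-related laboratory abnormalities that require discontinuation. It has no alternative-cause condition and no cholestasis clause.

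**The concern.** The conditions named as alternative causes are ones the protocol itself admits or calls general in its patients. Condition 3 asks about possible causes, not probable ones. In a patient with known cirrhosis or hepatitis C, a possible cause is apparent before the first dose. The hepatic management rules were adjusted for baseline liver disease, but the reporting definition was not.

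What is at stake is speed and visibility of reporting. An SAE goes to BMS within 24 hours or one business day (Section 15.2.3.1), and new related SAEs are reviewed monthly by the Data and Safety Monitoring Committee (Section 17.1). A non-serious event reaches BMS only in aggregate (Section 15.1.5). Liver injury is a stated interest of this trial: the 50 mg starting level was chosen "to observe hepatotoxicity in an HCC population", and Section 1.3.1 reports a treatment-related death from hepatic failure in the BMS-986205 programme.

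**Working it through.** The plan states no figure for this definition, so there is none to reproduce. The check sets the sections against each other.

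**Step 1. Entry limits against the DILI conditions**

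| DILI condition (15.1.8) | What entry allows (4.1, 5.5.3) | Effect |
|---|---|---|
| AST or ALT > 3 x ULN | up to 5 x ULN | met before dosing if entry value is above 3 and up to 5 x ULN |
| Bilirubin > 2 x ULN, ALP not raised | up to 2 x ULN | not met at entry by any eligible patient |
| No other apparent possible cause | treated HBV, untreated HCV, generally cirrhosis | read literally, not met |

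For condition 1, the multiple of baseline at which 3 x ULN is reached is 3 / b, where b is the entry value in ULN units: 3.0 for b = 1, 1.5 for b = 2, 1.0 for b = 3, 0.75 for b = 4 and 0.6 for b = 5. A patient entering at 5 x ULN still meets it after falling to just above 0.6 of baseline. Condition 1 is therefore over-inclusive for patients with raised entry values. Only condition 3 works towards the under-reporting described here.

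**Step 2. One event followed through the rules.** Take a hypothetical patient with untreated hepatitis C, AST 12 x ULN, bilirubin 4 x ULN and ALP not raised, judged drug-related.

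- Section 15.1.8: 12 > 3 and 4 > 2, so conditions 1 and 2 hold. Viral hepatitis is a possible cause, so on a literal reading condition 3 fails and the event is not a potential DILI.
- Section 6.1.4: both concurrent limits are exceeded, so the event is listed as requiring discontinuation.
- Section 5.6 hepatic DLT limits: 12 is above 10 but counts only if it lasts over 2 weeks; 12 is below 15; bilirubin 4 is below 5. These limits also apply only in the DLT window.
- Section 15.1.3: an SAE only if an ordinary criterion applies, such as hospitalization or the judgement-based important medical event.

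Being drug-related and being excluded by condition 3 are not contradictory. Section 15.1.2 lets an event be possibly related while underlying disease remains a candidate cause. Section 6.1.4 does not say whether possibly related counts as drug-related.

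**Step 3. Direction only, under assumptions.** Let q be the share of patients with an excluded cause and e the rate of events meeting conditions 1 and 2. Neither is in the documents. With condition 3 read literally, and e assumed the same in patients with and without an excluded cause, the chance of at least one qualifying case among the 17 MTD patients is 1 − (1 − e(1 − q))^17.

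| Assumed q | e = 5% | e = 10% |
|---|---|---|
| 0 (no exclusion) | 58% | 83% |
| 0.5 | 35% | 58% |
| 0.7 | 23% | 40% |
| 0.95 | 4% | 8% |
| 1.0 | 0% | 0% |

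For example, e = 10% and q = 0.7 gives 1 − 0.97^17 = 0.40. The spread shows that the result depends almost entirely on q and on the reading of condition 3.

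**The case against.** The strongest reply is that condition 3 concerns causes of the event, not diagnoses in the history. Patients enter with Child-Pugh A, without clinically significant ascites or encephalopathy, and with hepatitis B suppressed. An investigator may reasonably decide that stable disease does not explain a new, large rise. This stands: the literal reading is possible, not compulsory. But the text does not tell the investigator which reading to use, so the same event could be expedited or not depending on who reads it.

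The second reply is that hepatic events are captured elsewhere. This also stands in large part. There are DLT limits (5.6), discontinuation rules (6.1.4), ordinary SAE criteria regardless of relatedness (15.1.3), collection of all non-serious AEs (15.1.5.1), reporting of laboratory abnormalities that interrupt or stop drug (15.1.6), listings of out-of-range laboratory values (14.4), and monthly and weekly investigator meetings (17.1, 17.2). None of these guarantees expedited reporting of a case that meets no ordinary SAE criterion, and Section 15.1.6 gives no timeline.

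A reader might infer three stronger conclusions that the documents do not support:

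- That the hepatotoxicity signal will rarely qualify. No prevalence is given, and the literal reading is not the only one.
- That the 3 x ULN limit adds to under-reporting. Being above it at entry makes condition 1 easier to meet.
- That the primary safety endpoint is compromised. It is the CTCAE v5.0 profile, summarised from DLTs, AEs, SAEs and laboratory values, and escalation depends on Section 5.6 DLTs, not on Section 15.1.8.

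**Conclusion.** The definition is not adapted to the population it serves. On a literal reading of condition 3, a combined aminotransferase and bilirubin rise can require discontinuation under Section 6.1.4 and yet not be a mandatory potential-DILI SAE. The consequence is limited to one reporting route: the 24-hour or one-business-day report to BMS and the monthly committee review of related SAEs. Its size cannot be derived from the documents; the percentages in the working are illustrations under assumed q and e. That patients can meet condition 1 before dosing is a separate matter that errs towards over-reporting. This is a cheap improvement to safety reporting, not a defect that undermines the trial's design or its primary analysis.

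**What to change.** Amend condition 3 of Section 15.1.8 to say that cirrhosis, hepatitis B or hepatitis C present and stable at entry does not by itself count as an alternative cause, and that an event is excluded only when a new alternative cause is documented at the time of the event (for example biliary obstruction, a viral flare with rising viral load, or tumour progression in the liver).

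Reconcile Section 15.1.8 with Sections 5.5.3 and 6.1.4, and state whether an event that meets the concurrent limits of Section 6.1.4 is to be handled as potential DILI. Sections 5.5.3 and 6.1.4 also give different hepatic discontinuation limits. Which of those is right is not a matter for this point, but the reporting text needs one consistent reference.

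Keep the laboratory limits as they are. Making them relative to baseline could reduce reports: twice baseline from an entry AST of 4 x ULN is 8 x ULN, against the present 3 x ULN. It would also depart from the absolute limits in Section 6.1.4.

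The cost is an amendment to one reporting definition, with the BMS and IRB approvals that Section 16.6 requires, and somewhat more hepatic SAE reports to process. Liver tests, viral load where applicable, and scans are already in the study calendar. The change to condition 3 alters no treatment rule.
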